2. OBJECTIVES

2.1. Primary Objective

Evaluate the long-term efficacy and safety of roxadustat in the maintenance of Hb in dialysis and non-dialysis CKD subjects.

2.2. Secondary Objectives

Evaluate roxadustat doses and dose adjustments.

2.3. Exploratory Objectives

- Assess the effect of roxadustat on iron utilization parameters;
- Assess the effect of roxadustat on select biomarkers.

3. ENDPOINTS AND ASSESSMENTS

3.1. Efficacy

The efficacy endpoints in this study are:

- Mean monthly Hb values over time;
- Number (%) of subjects maintaining monthly (monthly defined as a 4-week interval) mean Hb at ≥ 10 g/dL during study participation upon correction (correction is defined as having achieved 2 consecutive Hb values of ≥ 10 g/dL);
- Number (%) of subjects maintaining Hb between 10-13 g/dL for at least 60% of scheduled Hb assessments after the first Hb value is 10 g/dL or higher.
- Composite rate of summarized rescue therapy events (transfusions, IV iron, ESAs) and rate of individual rescue therapy events;
- Number (%) of subjects with phlebotomies;
- Roxadustat weekly total doses over time;
- Dose adjustment frequencies;
- Hb variability;
- Number (%) of subjects withdrawn from the study due to inadequate efficacy.

3.2. Safety

Safety in this study will be assessed by evaluating the following:

- Vital signs, clinical laboratory values, ECG, and changes in physical examinations;
- AEs and SAEs.

3.3. Select biomarkers

Exploratory assessments in this study will evaluate the following parameters:

- Reticulocyte hemoglobin content (CHr);
- Highly sensitive C-reactive protein (hs-CRP);
- Hepcidin levels in serum;
- Additional exploratory biomarkers.

4. STUDY DESIGN

4.1. Description of the Study

This is an open-label, long-term maintenance study of roxadustat anemia therapy in dialysis and non-dialysis subjects with CKD who have completed the treatment period of an roxadustat anemia study in the U.S. Up to 50 non-dialysis, HD, and PD subjects will be enrolled in this study from up to 20 study centers throughout the U.S.

Subjects who received roxadustat in a previous study will continue to receive roxadustat at the same dose and frequency as they received at the end of the treatment period in their previous study, unless a dose adjustment is required.

Subjects who received placebo in their previous study may start treatment with roxadustat at starting doses according to their weight ([Appendix B](#)).

Subjects will receive study treatment for up to 312 weeks (6 years). Subjects enrolled in this study prior to Amendment 2 may continue treatment for up to an additional 1 year of treatment.

Subjects who received roxadustat in a previous study will return for study visits every 2 weeks for the first 104 weeks of treatment (including time on previous Phase 2/3 studies of roxadustat), and every 4 weeks thereafter, until the end of the treatment period.

Subjects who received placebo in their previous study will return for study visits weekly until their Hb level has stabilized to a range of 10.0 to 12.0 g/dL (± 2.0 g/dL) through 4 consecutive weeks. These subjects will then return for study visits every 2 weeks for the first 24 weeks of treatment, followed by every 4 weeks until the end of the treatment period.

After the end of treatment (defined as the last day a subject receives study drug) the subject will return for a follow-up visit 4 weeks later.

The baseline Hb value for efficacy analysis is defined as the mean of the central laboratory Hb value from the baseline visit at Day 1 (prior to receiving the first dose of study drug in this study), plus any other central lab Hb values within 15 days prior to Day 1.

Safety will be assessed by vital signs, physical examinations, clinical laboratory values (including liver function tests [LFTs] and complete blood counts [CBC]), electrocardiograms (ECGs), AEs and concomitant medication reporting. Clinical laboratory tests, including LFTs and Hb levels, may be assessed at additional times on unscheduled visits for safety reasons.

4.1.1. Control Groups

No control group will be included in this study.

4.2. Randomization and Treatment Assignment

4.2.1. Randomization Procedures

No randomization will be performed for this study.

4.2.2. Treatment Assignment

Subjects who received roxadustat in a previous study will continue to receive roxadustat.

Subjects who received placebo in their previous study may start treatment with roxadustat.

The roxadustat oral solid dosage (OSD) will be supplied in an open-label manner to all subjects.

4.3. Study Treatment

4.3.1. Dose and Schedule

Subjects who received roxadustat in a previous study will continue to receive roxadustat at the same dose and dosing frequency (TIW, BIW, or QW) as they received at the end of their last study, unless a dose adjustment is required.

Subjects who received placebo in their previous study will receive roxadustat by weight category as described in [Appendix B](#).

If treatment assignment is blinded at the time of enrollment, the subject has been on a stable dosing regimen for at least 2 months and if the last dose is lower than the starting doses described in [Appendix B](#), the subject may continue on the current dosing regimen.

4.3.2. Dose Adjustments

Guidelines for dose adjustments are provided in C. In general:

- The Hb thresholds for dose adjustments are < 10 g/dL for dose increases and \geq 12 g/dL for dose reductions
- Dose adjustment rules are based on changes in Hb values over 4 weeks and whether the Hb target has been reached or exceeded.
- Dose increases and decreases are pre-set at the dose steps described in [Appendix A](#).
- The maximum dose is 3.0 mg/kg.
- The time interval between dose adjustment reviews should be 4 weeks, except in the event of excessive hematopoiesis (when the subject's dose should be reduced), or rapidly declining Hb (when the subject's dose should be increased). For example, even if a subject's dose is not increased or decreased following a dose adjustment review visit, the next dose adjustment review will be 4 weeks after the last dose adjustment review.
- For subjects who received placebo in their previous study, no dose adjustment will occur from Weeks 1 through 4 except in the event of excessive hematopoiesis or rapidly declining Hb.
- For subjects who received roxadustat, or blinded study drug, and on a stable dose for the past 2 months, in a previous study, dose adjustment review will occur 4 weeks from the last dose adjustment review in the previous study.
- During the course of the study, the dose and the dosing frequency may be changed to optimize efficacy and tolerability based on the clinical judgment of the investigator and study medical monitor.

In the event of an extenuating clinical circumstance (e.g., recent bleeding, disruption of dosing due to hospitalization or vacation, etc.), the investigator may dose a subject outside of the dose adjustment parameters provided this has been discussed with the study medical monitor.

Dose Frequency Adjustments should be done according to [Appendix C](#).

Dose Adjustment for Excessive Hematopoiesis

At any time during the treatment period, if Hb increases by > 2.0 g/dL in 2 weeks that is not due to an RBC transfusion the dose should be reduced by one dose step ([Appendix A](#)).

If there are clinical concerns for a subject's excessively high Hb value outside the dose adjustment intervals (as described in [Appendix A](#)), the investigator may adjust the dose immediately; the investigator may also decide to perform a therapeutic phlebotomy in addition to the dose adjustments—these situations should be documented and discussed with the study medical monitor whenever possible.

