APPENDIX C. DOSE ADJUSTMENT GUIDELINES FOR ROXADUSTAT

All dose adjustments should be based on Hb values using a point-of-care device, such as HemoCue® or CritLine®. In the event that the central lab Hb value of the site visit is significantly different and the dose adjustment decision based on the HemoCue® / CritLine® value is being re-considered, the Medical Monitor should be contacted, if possible.

Dose adjustment reviews will occur on Week 4, and at intervals of every 4 weeks thereafter (Weeks 8, 12, 16, etc.), except in the event of excessive hematopoiesis, in which case doses may be adjusted at any time. In such cases, dose adjustment reviews are resumed at 4-week intervals. For example, if the subject's Hb increases > 2.0 g/dL from Week 1 to Week 3, the subject's dose is reduced by one dose step at Week 3. The next dose adjustment review should occur 4 weeks later at Week 7. If the dose adjustment interval falls on a non-study visit week (starting Week 4), the dose adjustment review should be performed at the next scheduled study visit if a dose adjustment was not required at the previous visit. For example, if a subject's visit is scheduled for Weeks 6 and 8, and the dose adjustment would occur at Week 7, then the dose adjustment should be evaluated at the Week 8 visit.

All subjects will be dosed orally TIW during the Treatment period. During the course of the study, the dose and the dosing frequency may be changed to optimize efficacy and tolerability based on the clinical judgment of the investigator and study medical monitor. If a subject requires < 20 mg TIW (ie, < 60 mg per week) to maintain the target Hb level, the dosing frequency should be reduced in a step-wise fashion eg, TIW to BIW, BIW to QW, QW to Q-2 Week etc. The Medical Monitor should be notified as soon as possible of such dose change. The maximum roxadustat dose is 3.0 mg/kg per dose or 400 mg (whichever is lower).

The following scenarios are defined as “excessive hematopoiesis”;

Hb increases by > 2.0 g/dL at any time within a 4 week period: reduce the dose by one dose step.

Hb reaches or exceeds 13 g/dL: hold dosing, check Hb weekly. Resume dosing when Hb < 12.0 g/dL (for US subjects central lab Hb value preferred), at a dose that is reduced by two dose steps.

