For subjects on prolonged dose-hold, with stable (not dropping) Hb, PI may use discretion to schedule less frequent visits. Anytime Hb is assessed via HemoCue®/CritLine®/local lab, a central lab Hb should be obtained as well.

Given the complexity in roxadustat dose adjustments, and the need to take into account the various clinical parameters in roxadustat dose titration, one would not consider it a protocol deviation when study subjects are dosed based on their clinical circumstances, whether or not it is concordant with the roxadustat dose adjustment guidelines unless it was related to “excessive hematopoiesis” (eg, Hb ≥ 13 g/dL, requiring a dose hold) or “Overdose” (prescribed > 3.0 mg/kg per dose or 400 mg per dose whichever is lower)

Roxadustat Dose Adjustment Rules				
Change in Hb from 4 weeks earlier (g/dL)	Hb < 10.5 g/dL	Hb 10.5 to 11.9 g/dL	Hb 12.0 to 12.9 g/dL	Hb ≥ 13.0 g/dL
< -1.0	↑	↑	No change	Hold, then resume dosing when: Hb < 12 g/dL, at a dose that is reduced by two dose steps Subjects are to return weekly to monitor Hb until dosing can be resumed**
-1.0 to 1.0	↑	No change	↓	
> 1.0	No change	↓	↓	

Dose Adjustment for Excessive Hematopoiesis: At any time during the Treatment Period if Hb increases by >2.0 g/dL within 4 weeks, the dose should be reduced by one dose step. ** For subjects on prolonged dose-hold, with stable (not dropping) Hb, PI may use discretion to schedule less frequent visits. Anytime Hb is assessed via HemoCue®/CritLine®/local labs, a central lab Hb should be obtained as well
 
Dose Increases and Reductions: Dose increases (↑) and reductions (↓) are preset to dose steps. The dose steps are as follows: 20, 40, 50, 70, 100, 150, 200, 250, 300, and 400 mg. Example: A dose increase at a dose of 70 mg results in 100 mg as the new dose. A dose reduction at a dose of 150 mg results in 100 mg as the new dose. Note: Maximum dose capped at 3.0 mg/kg per dose or 400 mg, whichever is lower.
 
*Transition from Correction to Maintenance Phase will occur once the central laboratory Hb value is ≥ 11 g/dL and ≥ 1 g/dL from baseline

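### The hemoglobin rise that forces a dose cut is timed over 2 weeks in Protocol Section 4.3.2 but over 4 weeks in the synopsis and Appendix C, and the stated maximum treatment duration also conflicts

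*Protocol*

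**What the plan says.** **Rise rule.** Section 4.3.2, under its own subheading on excessive hematopoiesis, cuts the dose one step "if Hb increases by > 2.0 g/dL in 2 weeks that is not due to an RBC transfusion", and cites Appendix A for the step. The Appendix C text says "Hb increases by > 2.0 g/dL at any time within a 4 week period: reduce the dose by one dose step"; the synopsis uses the same wording. The note to the Appendix C table repeats it: "if Hb increases by >2.0 g/dL within 4 weeks, the dose should be reduced by one dose step". None of these three places excludes rises due to transfusion.

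**Status of the summary in 4.3.2.** The section opens with "Guidelines for dose adjustments are provided in C. In general" and then lists bullets. One reads "The Hb thresholds for dose adjustments are < 10 g/dL for dose increases" and sets reductions at 12 g/dL or above. The next says "Dose adjustment rules are based on changes in Hb values over 4 weeks and whether the Hb target has been reached or exceeded". The Appendix C grid has its lowest Hb column below 10.5 g/dL, not below 10.

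**Deviation waiver.** Appendix C says "one would not consider it a protocol deviation when study subjects are dosed based on their clinical circumstances". This covers dosing that departs from the guidelines, with two exceptions: excessive hematopoiesis and overdose.

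**Pointers.** Two dose-step references in 4.3.2, and the synopsis line on dose-adjustment rules, cite Appendix A. Appendix A is the schedule of assessments; the steps and the grid are in Appendix C.

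**Duration.** Section 4.1 and SAP Section 3 give 312 weeks (6 years). Footnote a of Appendix A gives 260 weeks (5 years). The synopsis gives 416 weeks, labelled 6 years, under study periods, and a total of 8 years under study design. The extra year is tied to Amendment 1 in the synopsis and to Amendment 2 in Section 4.1.

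**The concern.** The rise rule is a safety limit on how fast hemoglobin may climb. A site working from Section 4.3.2 and a site working from Appendix C can see the same values and act differently: one leaves the dose alone, the other cuts it. Following the Appendix A pointer in 4.3.2 leads to neither the 4-week rule nor the dose steps.

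The waiver adds to this. Off-guideline dosing is not a deviation, except where excessive hematopoiesis or overdose is involved, and Appendix C lists the rise above 2.0 g/dL as one form of excessive hematopoiesis. The window therefore bears on whether leaving a dose unchanged counts as a deviation.

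The secondary objective is to evaluate doses and dose adjustments, and the SAP reports dose increases, decreases and holds. A reader of those counts needs to know which rule was in force. The duration conflict leaves the exposure ceiling unclear.

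**Working it through.** **1. The rise rule side by side**

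| Place in the protocol | Rise | Window | Transfusion excluded |
|---|---|---|---|
| Section 4.3.2 | > 2.0 g/dL | 2 weeks | yes |
| Synopsis | > 2.0 g/dL | 4 weeks | no |
| Appendix C text | > 2.0 g/dL | 4 weeks | no |
| Appendix C table note | > 2.0 g/dL | 4 weeks | no |

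The worked example in the synopsis and Appendix C (a rise from Week 1 to Week 3) spans 2 weeks and fits either rule, so it does not settle the matter.

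**2. Trigger rate for a steady rise** (threshold / window)

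- Section 4.3.2: 2.0 / 2 = 1.0 g/dL per week.
- Appendix C: 2.0 / 4 = 0.5 g/dL per week.

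Every rise that meets 4.3.2 also meets Appendix C. The reverse fails in two cases: a rise that exceeds 2.0 g/dL only over more than 2 and up to 4 weeks, and a rise caused by transfusion.

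**3. What the 4-week rule adds at a scheduled 4-week review.** A rise above 2.0 g/dL falls in the grid row for changes above 1.0:

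| Current Hb (g/dL) | Grid action | Does the 4-week rule add a cut? |
|---|---|---|
| < 10.5 | no change | yes |
| 10.5 to 11.9 | reduce | no |
| 12.0 to 12.9 | reduce | no |
| ≥ 13.0 | hold | no |

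The rule therefore adds a cut only when current Hb is below 10.5, which requires Hb below 10.5 − 2.0 = 8.5 four weeks earlier. Two examples:

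- 8.2 to 10.3: rise 10.3 − 8.2 = 2.1; if steady, 2.1 / 2 = 1.05 per 2 weeks. This does not meet 4.3.2. The grid alone gives no change, and the 4-week rule gives a one-step cut.
- 7.7 to 9.8: rise 2.1, with the same result.

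**4. Between reviews.** The grid is applied at 4-week reviews, while the rise rule applies at any time. Between reviews, a rise above 2.0 g/dL that takes more than 2 and up to 4 weeks is a cut under Appendix C and not under 4.3.2, at any Hb below the 13 g/dL hold.

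**5. Summary thresholds.** At a stable Hb of 10.0 to 10.4, the grid increases the dose, but the 4.3.2 bullet does not, because it starts increases below 10.

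**6. Duration** (weeks / 52). The synopsis figure of 416 weeks for 6 years does not reproduce: 6 × 52 = 312.

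- Appendix A: 260 / 52 = 5.0 years.
- Section 4.1 and SAP: 312 / 52 = 6.0 years.
- Synopsis: 416 / 52 = 8.0 years.

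Against 312 weeks, the synopsis is 416 − 312 = 104 weeks too long and Appendix A is 312 − 260 = 52 weeks too short.

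**The case against.** The best defence is that a site can satisfy both rules by cutting at the 4-week rise. Section 4.3.2 defers to Appendix C at its start, does not forbid a cut for a slower rise, and lets the investigator adjust at once when a high Hb is a clinical concern. The waiver sits in Appendix C, so its exception most naturally uses that appendix's 4-week definition, and the example it gives is the hold at 13 g/dL. The study is uncontrolled, unpowered and descriptive. The SAP text specifies no deviation summary; its table specifications are in a separate document.

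Much of this stands, and it limits the consequence. It does not remove the conflict. The deferral introduces the bullet list, whereas the rise rule comes later under its own subheading, applies at any time during treatment, and points to Appendix A. Its transfusion exclusion has no counterpart elsewhere.

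Four stronger readings are tempting, and the documents do not support them:

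- **A wide gap.** From the 12 g/dL reduction threshold in 4.3.2, a reader might infer that the windows differ at a review for any current Hb below 12 (below 10.0 four weeks earlier). That treats the summary bullet as the whole rule and overlooks the grid, which already reduces from 10.5 upward after such a rise.
- **A frequency.** A reader might compare the trigger rates with the rise of about 2 g/dL in six weeks in Section 1.6.2. That figure is from newly initiated dialysis subjects in study 053. The 15 entrants came from studies 040 and 041, and all had already received roxadustat.
- **Past deviations.** A reader might class every uncut 4-week rise as a deviation. That would penalise sites that followed Section 4.3.2 as written.
- **Two extra years of treatment.** A reader might take 8 years as permitted. The 416-week figure carries a 6-year label, Section 4.1 and the SAP agree on 312 weeks, and the amendment summary shows that 312 was intended.

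**Conclusion.** The conflict is real and worth correcting, but its reach is limited. A safety dosing rule has two windows that differ by a factor of two in steady-rise rate, and only one version excludes transfusions. Under the Appendix C grid, the 4-week rule changes the action at a scheduled review only for Hb below 10.5 g/dL after a value below 8.5. Between reviews, the windows can differ at any Hb below 13. Separately, the current protocol carries three maximum durations: 5, 6 and 8 years.

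The conclusion rests on reading the grid as the operative rule at reviews, as the deferral in 4.3.2 indicates. The documents do not show how often such rises occurred among the 15 previously treated entrants, or that any dosing decision was affected. No count or estimate defined in the SAP changes. What is at stake is consistent dosing under a safety rule, fair classification of deviations, and an accurate account of the regimen and exposure limit in the study report.

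**What to change.** In the protocol:

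- State that Appendix C governs dose adjustment.
- In Section 4.3.2, change the 2-week window to within 4 weeks, and replace the bullet with the 10 and 12 g/dL thresholds by a reference to the Appendix C grid.
- Redirect the two dose-step pointers in 4.3.2, and the synopsis dose-adjustment line, from Appendix A to Appendix C.
- Decide whether rises due to RBC transfusion are excluded, and say so identically in 4.3.2, the synopsis and Appendix C.
- Set the maximum to 312 weeks (6 years) for subjects enrolled before Amendment 2 and 52 weeks for those enrolled under it, in both synopsis places and in footnote a of Appendix A.

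If treatment is complete, disclose the conflict and the governing duration in the study report. Flag rises above 2.0 g/dL under both windows, and do not retrospectively class dosing that followed Section 4.3.2 as a deviation.

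The cost is a clarifying amendment or administrative letter. After completion it is a short paragraph in the study report and a flag derived from Hb values already collected. No new patients or visits are needed.

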4.4. Concomitant Medications, Procedures and Nondrug Therapies

4.4.1. Concomitant Medications

Concomitant medications are any prescription or over-the-counter preparations (including herbal products and “natural remedies”) used by a subject while participating in this clinical trial.

For all concomitant medication use, the study site must provide an indication for its use. If the stated indication is a nonspecific condition, e.g., “rash,” documentation of the condition, as specific as possible, must be provided by the subject's primary care physician and maintained in the subject's clinical study records as source documentation.

4.4.2. Contraception

Female subjects of childbearing potential must agree to use a medically acceptable form of birth control (e.g., oral contraceptive pills, depot progesterone, or intrauterine device). The above list is not comprehensive. Abstinence alone suffices as adequate contraception. Male subjects with sexual partners of childbearing potential who are not using birth control (as described above) must use contraception (e.g., condom) if not surgically sterile (i.e., vasectomy). Contraceptive methods must be practiced from the time informed consent is signed and through at least 1 month after the last dose of study drug.

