5.2. Exclusion Criteria

1. Subjects assigned to epoetin alfa in a previous ongoing roxadustat anemia study
2. Pregnant or breastfeeding females
3. Females of childbearing potential, unless using contraception as detailed in the protocol; male subjects with sexual partners of childbearing potential who are not on birth control unless the male subject agrees to use contraception
4. Subjects who received roxadustat in a previous study that did not demonstrate adequate hemoglobin response per the investigator's clinical judgment
5. Any medical condition that in the opinion of the investigator may pose a safety risk to a subject in this study, or which may interfere with study participation

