7.2. Post-Treatment Follow-Up Period

The Follow-up Period begins on the week after the last dose of study treatment, and continues for 4 weeks.

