8. SUBJECT DISCONTINUATION

Subjects may withdraw from the study at any time. Withdrawn subjects should be strongly advised to complete the 4-week Follow-up Period procedures as outlined in the Schedule of Study Assessments in [Appendix A](#). The appropriate documentation must be entered on the Study Termination CRF. Subjects should be discontinued from the study for any of the following reasons:

- Significant noncompliance with study procedures, as determined by principal investigator and study medical monitor;
- Subject no longer consents to participate in the study;
- Physician decision that it is in the best interest of the subject to be withdrawn from the study;
- Need for ESA rescue therapy due to lack of efficacy and/or lack of tolerability to roxadustat;
- Study medical monitor and principal investigator agree that a subject's intercurrent illness is significantly interfering with study assessments;
- The study is terminated by FibroGen for any reason or by the DMC due to safety concerns;
- Subject is lost to follow-up for the duration of the study;
- At FibroGen's discretion;
- Subject is found to be pregnant;
- Death.

Subjects who withdraw from the study will be followed for AEs as described in [Section 11](#) of this protocol. The reason for withdrawal from the study will be documented in the CRFs.

Women of childbearing potential who withdraw from this study will continue contraception for at least 12 weeks following the last roxadustat administration. Male subjects with partners of childbearing potential must agree to use a medically acceptable method of contraception during the trial and for at least 12 weeks following the last roxadustat administration.

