11.3.5. Pregnancies: Reporting and Follow-up of Subjects

A pregnancy in a female subject or a male subject's female partner must be confirmed by a positive serum beta-hCG test. If a female subject or the female partner of a male subject becomes pregnant while the subject is receiving study treatment or within 3 months after the last dose of study treatment, a Pregnancy Report Form must be completed and submitted to FibroGen within 24 hours of the investigator learning of the pregnancy. A pregnant subject is immediately withdrawn from receiving study treatment. The investigator must follow the pregnancy to completion to ascertain both its outcome and whether any AEs occur.

Pregnancy itself is not an AE. Abortion, whether accidental, therapeutic, or spontaneous, should always be classified as serious, recorded on an SAE Report Form, and reported to FibroGen within 24 hours of the investigator learning of the event. Similarly, any medically significant congenital anomaly/birth defect in a child born to a female subject or the female partner of a male subject exposed to the investigational product should be recorded and reported as an SAE.

The outcome of the pregnancy must be reported by the investigator on a Pregnancy Outcome Report Form, which should be sent to FibroGen within 24 hours of the investigator learning of the outcome.

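### Protocol 4.4.2 and Section 8 set different minimum periods of post-dose contraception for women who withdraw and for men with partners of childbearing potential

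*Protocol*

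**What the plan says.** Protocol 4.4.2 is the section devoted to contraception. It places the obligation on female subjects of childbearing potential. It also places it on male subjects who are not surgically sterile and whose partners of childbearing potential are not using birth control. One time clause then covers both sexes: contraception runs from the signing of consent "through at least 1 month after the last dose of study drug".

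Section 8, on subject discontinuation, ends with two sentences on the same subject. The first reads: "Women of childbearing potential who withdraw from this study will continue contraception for at least 12 weeks following the last roxadustat administration". The second concerns men whose partners could become pregnant and says that they "must agree to use a medically acceptable method of contraception during the trial and for at least 12 weeks following the last roxadustat administration". The first is limited to those who withdraw; the second carries no such limit.

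Three other places bear on the point without settling it:

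- Section 11.3.5 makes a pregnancy in a subject or a subject's partner reportable if it begins during treatment or "within 3 months after the last dose of study treatment".
- Exclusion criterion 3 in Section 5.2 gives no duration. It excludes "Females of childbearing potential, unless using contraception as detailed in the protocol".
- Section 7.2 fixes the follow-up: "The Follow-up Period begins on the week after the last dose of study treatment, and continues for 4 weeks".

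The SAP does not mention contraception.

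**The concern.** Two current sections of one protocol give different minimums for some of the same people. A site looking for the contraception rule would naturally turn to 4.4.2, which has the shorter period. The longer one sits at the end of the section on discontinuation. A subject advised from 4.4.2 could stop after about a month, in good faith, and be out of compliance with Section 8.

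What is at stake is a patient-safety instruction, and the study schedule offers little chance to correct wrong advice later. The follow-up visit is 4 weeks after the last dose (Protocol 4.1 and Appendix A, note b), adverse-event reporting ends 28 days after the last treatment (11.3.1), and the last scheduled hCG test is at the termination or early-termination visit (7.1.1.1.6 and Appendix A). After that, the subject has only the instruction already given.

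**Working it through.** The protocol gives no figure of its own for this difference, so there is nothing to reproduce. The check is a comparison of the texts with a conversion to days.

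**Inputs**

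- 4.4.2: 1 month = 28 to 31 days, depending on the calendar month.
- Section 8: 12 weeks = 12 × 7 = 84 days.
- 11.3.5: 3 months. The shortest run of three calendar months is February to April in a common year, 28 + 31 + 30 = 89 days.
- Follow-up: 4 weeks = 4 × 7 = 28 days.

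**Difference between the minimums**

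- Against the longest month: 84 − 31 = 53 days.
- Against the shortest month: 84 − 28 = 56 days.

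**Who is covered by which sentence**

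| Group | 4.4.2 | Section 8 | Result |
|---|---|---|---|
| Women of childbearing potential who complete treatment | 1 month | no sentence applies | one rule, no contradiction |
| Women of childbearing potential who withdraw | 1 month | 12 weeks | minimums differ by 53 to 56 days |
| Men, not surgically sterile, partner of childbearing potential not using birth control | 1 month | 12 weeks | minimums differ by 53 to 56 days |
| Other men with a partner of childbearing potential (partner uses birth control, or the man is surgically sterile) | no obligation stated | 12 weeks | the sections differ on who is covered |

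The direct conflict of duration is therefore in the second and third rows. The fourth row is a related mismatch: Section 8 names all men with partners of childbearing potential, while 4.4.2 makes exceptions.

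**Where the disputed period falls**

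- It runs from about day 28 to 31 after the last dose to day 84.
- The follow-up visit is due at day 28. If the follow-up period is counted from the week after the last dose, it ends at the latest at day 7 + 28 = 35. On that reading 84 − 35 = 49 days still lie beyond it.
- Day 84 comes before day 89, so the whole disputed period lies inside the pregnancy-reporting window.

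**The case against.** The strongest reply is that both periods are floors. Contraception for 12 weeks or more satisfies both sections, so a site can comply with the whole protocol. That is correct, and the two rules are not mutually exclusive. It does not remove the problem: a minimum tells the site what is enough, the sections disagree on what is enough, and meeting the shorter floor can breach the longer one.

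A second reply is that Section 8 deals only with discontinuation. This stands for women, because their sentence is restricted to those who withdraw. For men it rests on the section's title alone; the sentence itself speaks of the trial as a whole and does not mention withdrawal.

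A third is that few people are affected. The SAP (Section 3) reports that fifteen subjects entered. The documents do not say how many belonged to either affected group, so the number lies somewhere between none and fifteen. This limits the practical reach but leaves the contradiction in place.

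A reader might also infer more than the documents support:

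- *Every subject receives conflicting instructions.* Women who complete treatment have only the 1-month rule.
- *There are three conflicting contraception periods.* Section 11.3.5 says how long pregnancies must be reported. A reporting window need not equal a contraception period.
- *Eligibility changes with the section that is read.* Exclusion criterion 3 turns on using, or agreeing to use, contraception. No subject is shown to become eligible or ineligible because of the post-dose duration. At most, the period agreed to at entry is unclear.
- *The consent form is wrong.* It was not available for review and may already state one period.

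**Conclusion.** This is an internal inconsistency in the current protocol text. For women of childbearing potential who withdraw, and for men covered by both sections, the stated post-dose minimums differ by 53 to 56 days, and a subject who follows only 4.4.2 can stop while Section 8 still requires contraception. The size rests on reading a month as 28 to 31 days and on taking the sentence about men as written, without a withdrawal limit. If that sentence were meant for withdrawals only, the conflict would narrow to men and women who withdraw.

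For women who complete treatment there is no contradiction. The protocol leaves open whether a shorter period for completers than for women who withdraw is deliberate: it gives no reason, and 4.4.2 does not mention it.

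No endpoint, analysis population or estimate is affected. The point deserves correction because it concerns patient safety and is easy to put right. Nothing here implies that either period is the right one.

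**What to change.** The sponsor should reconcile 4.4.2 and Section 8 so that:

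1. each of three groups has one stated post-dose period: women who complete treatment, women who withdraw, and men with partners of childbearing potential;
2. both sections describe in the same way who is covered, including men whose partners use birth control and men who are surgically sterile;
3. any intended difference between women who complete and women who withdraw is stated as intended in 4.4.2.

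The sponsor should then confirm that the consent text gives the same periods, and check that the result sits sensibly beside the 4-week follow-up and the reporting window in 11.3.5. The choice of period is a clinical decision for the sponsor.

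The cost is a protocol clarification and, if the consent text differs, matching wording there. The SAP needs no change.
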